7. CLINICAL ASSESSMENTS

The study procedures and assessments are presented in Section 10 of the protocol and the schedule of assessments is presented in Section 5.

8. DEFINITIONS AND CONVENTIONS

8.1. Calculations Using Dates

Age at informed consent is calculated as the integer part of (date of informed consent – date of birth)/365.25.

Duration of treatment (days) is defined as (last dose date + 7 – first dose date). If a subject dies within 7 days of the last dose of study treatment, the duration of treatment is calculated as (death date – first dose date + 1).

Study day is defined as:

- Event Date – First Dose Date + 1 if the event date is on or after the first dose date
- Event Date – First Dose Date if the event date is before the first dose date

8.2. Study Visits

8.2.1. Baseline

The analysis value for urine albumin/creatinine ratio is defined as the average of all the values obtained at a timepoint. The planned number of urine albumin/creatinine ratios is three at each scheduled timepoint. The baseline value of the urine albumin/creatinine ratio is defined as the average of the analysis values from the two screening visits. The analysis value for urine protein/creatinine ratio is defined in the same fashion.

For all other study variables, the baseline value is defined as the last non-missing value prior to the first study drug administration.

8.2.2. Day 1

Study Day 1 is defined as the first dose date of study treatment.

8.2.3. Visit Windows Relative to the First Dose of Study Treatment

Table 2: Visit Windows (Days)

Visit	Target Day	Visit Window (Days) ¹
Day -28 (Screening Visit 1)	-28	-28 to -21
Day -14 (Screening Visit 2)	-14	-20 to -1
Day 1 (Treatment Visit 1)	1	1
Day 2 (Treatment Visit 1) ²	2	2 to 3
Day 4 (Treatment Visit 1) ²	4	4
Day 8 (Treatment Visit 2)	8	2 to 11
Day D (Treatment Visit T, T>2)	D (15, 22, ..., 78)	D – 3 to D + 3
Day 85 (Follow-up Visit 1)	85	82 to 102
Day 120 (Follow-up Visit 2)	120	103 to 148
Day 176 (Follow-up Visit 3)	176	149 to 221
Day 267 (Follow-up Visit 4)	267	222 to 312
Day 358 (Follow-up Visit 5)	358	313 to 403
Day 449 (Follow-up Visit 6)	449	404 to 494

Table 2: Visit Windows (Days) (Continued)

Visit	Target Day	Visit Window (Days) ¹
Day 540 (Follow-up Visit 7)	540	495 to 585
Day 631 (Follow-up Visit 8)	631	586 to 676
Day 722 (Follow-up Visit 9)	722	≥ 677

¹ If there are more than 1 non-missing assessments in the same visit window, the closest one to the target day will be used in the analysis. If there are 2 assessments that are equally spaced from the target day, the latter will be used in the analysis.

² Day 2 and Day 4 apply to PK only.

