10.1.16. Unscheduled Visits

Unscheduled visits and assessments for subject safety should be documented and recorded.

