5.2. Cohorts 3 Re-Treatment

Period	Treatment (12 Weeks)											Follow-Up (1 Week)
Visit	RT1			RT2, RT3	RT4	RT5	RT6, RT7	RT8	RT9	RT10, RT11	RT12	RT FU
Day	1	2	4	8,15	22	29	36,43	50	57	64,71	78	85
				(+/- 2)								(+/- 3)
Week	1			2-3	4	5	6-7	8	9	10-11	12	13
Confirm Eligibility and Informed Consent	X											
Vital Signs												X
Vital Signs pre-dose	X			X	X	X	X	X	X	X	X	
Vital Signs post dose: 30 min				X	X	X	X	X	X	X	X	
Vital Signs post dose: 30 min, 1 hr	X											
ECG pre-dose	X										X	
ECG post dose	X ⁸										X	
Dispense urine collection kit ¹					X			X			X	
Collect Urine Samples from urine collection kit ²						X			X			X
24 Urine protein collection ¹												X
Urine for inflammatory biomarkers ⁷	X			X					X			X
Urinalysis ^{3,7}	X			X					X			X
Blood Sample Collection: Chemistry, Hematology, Coagulation, Cystatin C ^{4,7}	X			X		X			X			X
Calculation of eGFR using the MDRD formula												
Pregnancy Test – females of child bearing potential ⁶	X					X			X			X
Study Drug Administration	X			X	X	X	X	X	X	X	X	
Research Sampling ⁷	X			X		X			X			X
PK Sampling												X
PK Sampling pre-dose ⁷	X			X		X			X		X	
PK Sampling post dose: 5 minutes and 2 hours	X										X	
PK Sampling post dose: 24 hours		X										
PK Sampling post dose: 72 hours			X									
PD Sampling												X
PD Sampling pre-dose ⁷	X			X		X			X		X	
PD Sampling post dose: 2 hours	X										X	
ADA Sampling pre dose	X					X			X			X
Adverse Events	X	X	X	X	X	X	X	X	X	X	X	X
Concomitant medications/therapies	X	X	X	X	X	X	X	X	X	X	X	X

SCR = screening; ECG = electrocardiogram; HIV = human immunodeficiency virus; PD = pharmacodynamics; PK = pharmacokinetics; ADA = anti-drug antibody

1. Instruct the subject on how to collect and provide supplies.
2. Collect first void urine on each of three mornings, 1st void urine samples.
3. Urinalysis tests include color, specific gravity, pH, glucose, protein, bilirubin, urobilinogen, blood, ketone, nitrite, leukocyte esterase and microscopic if required (red blood cells, white blood cells and bacteria).
4. The following laboratory assessments will be performed in this study:
 - Chemistry tests include glucose, urea nitrogen, creatinine, total protein, albumin, total bilirubin, alkaline phosphatase, ALT, AST, calcium, sodium, potassium, chloride, and bicarbonate

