12. EFFICACY ANALYSIS

12.1. General Considerations

All data summaries will be descriptive in nature and efficacy summaries will be presented by disease group, cohort and treatment. Summary statistics for continuous variables will include number of subjects, mean, median, standard deviation, minimum, and maximum. For categorical variables, frequencies and percentages will be provided. Baseline value will be calculated according to Section 8.3.1. All confidence intervals will be constructed at the two-sided 95% confidence level.

The data collected during the re-treatment period for the rollover subjects in Cohort 1 and Cohort 2 will be presented in listings. Because the open-label OMS721 dose is different from the original OMS721 dose and re-treatment is optional, statistical analyses for Cohort 1 and Cohort 2 will include the data collected in the initial treatment period and the initial follow-up period only. Statistical analyses for Cohort 3 will include the subjects who are randomized in Cohort 3 only. All data collected for the randomized subjects in Cohort 3 will be summarized.

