13.5. Routine Laboratory Data

Summary statistics for actual values and for change from baseline will be tabulated as appropriate for laboratory results by scheduled visit, disease group, cohort and treatment. Subjects with laboratory values outside of the normal reference range at any post-baseline safety assessment will be listed by disease group, cohort and treatment.

Shifts from baseline laboratory values (normal/abnormal) will be tabulated by disease group, cohort and treatment.

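### SAP Table 2 has no rows for Cohort 3 re-treatment visits: applied literally, it files on-drug safety values under follow-up visits and keeps at most 2 of 5 chemistry/haematology sets and 2 of 13 vital-sign visits per course

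*SAP*

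**What the plan says.** - **Windows.** Table 2 of the SAP stands under the title "Visit Windows Relative to the First Dose of Study Treatment". From Day 82 its rows (FU1 to FU9) follow one another without a gap. Footnote 1 reads: "If there are more than 1 non-missing assessments in the same visit window, the closest one to the target day will be used"; if two are equally distant, the later one is taken. The only restriction by type of test is footnote 2: "Day 2 and Day 4 apply to PK only".
- **Re-treatment visits.** SAP 5.2 gives each course its own visits, RT1 to RT12 and RTFU, on its own Day 1 to Day 85 scale. The row "Blood Sample Collection: Chemistry, Hematology, Coagulation, Cystatin C" is marked at RT1, RT2, RT5, RT9 and RTFU (the footnote removes RT3). Vital signs are marked at all 13 visits. None of these visits appears in Table 2.
- **Safety tables.** SAP 13.5: "Summary statistics for actual values and for change from baseline will be tabulated as appropriate for laboratory results by scheduled visit". SAP 13.6 treats vital signs in the same way. SAP 13.5 also lists subjects with out-of-range laboratory values at any post-baseline assessment; SAP 13.6 specifies no listing for vital signs.
- **Cohort 3 data.** SAP 12.1, in the efficacy section: "All data collected for the randomized subjects in Cohort 3 will be summarized". The same paragraph confines rollover subjects' re-treatment data to listings.
- **Unscheduled visits.** Protocol 10.1.16: "Unscheduled visits and assessments for subject safety should be documented and recorded". The SAP does not say whether such values enter the laboratory or vital-sign tables.

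**The concern.** Safety and tolerability, including laboratory tests and vital signs, is the sole primary endpoint (SAP 6). Open-label re-treatment is the only OMS721 exposure for subjects randomized to vehicle in Cohort 3, and the only repeat exposure for those randomized to OMS721.

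A programmer who follows the SAP as written has one windowing rule, and it assigns every post-Day-82 value to a follow-up row. Two things then go wrong. Values taken during weekly dosing are labelled as follow-up values. And the value kept is the one nearest a day unrelated to dosing in the course, not the most abnormal one. Vital signs show the labelling problem most clearly: SAP 5.1 schedules none at FU3 to FU9, so any row with those labels would hold only re-treatment or unscheduled values.

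**Working it through.** **Inputs.** Table 2 targets and bounds (SAP 8.2.3). Chemistry/haematology at RT1 + 0, 7, 28, 56 and 84 days (5 sets) and vital signs at RT1 + 0, 7, …, 84 days (13 visits) (SAP 5.2). Tolerances: ±3 days for FU1, FU2 and RTFU, ±14 for FU3 to FU9, ±2 for RT visits (SAP 5.1 and 5.2; Protocol 10.1.18). Follow-up visits falling inside a course are skipped (end of Protocol 10.1.11). The calculation assumes that RT visits are mapped into Table 2.

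**Table 2 reproduced.** Bounds are midpoints between target days: (78+85)/2 = 81.5, (85+120)/2 = 102.5, (120+176)/2 = 148, (176+267)/2 = 221.5, and so on. These match the stated lower bounds 82, 103, 149, 222, etc.

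| Row | Window | Days |
|---|---|---|
| FU1 | 82–102 | 21 |
| FU2 | 103–148 | 46 |
| FU3 | 149–221 | 73 |
| FU4 to FU8 | e.g. 222–312 | 91 each |
| FU9 | from 677 | open-ended |

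**One course, visits on target.** RT1 on Day 134 gives laboratory sets on Days 134, 141, 162, 190 and 218.
- FU2 row: Days 134 and 141 are 14 and 21 days from 120; the FU2 visit itself is 0 days away and is kept.
- FU3 row (the FU3 visit, Day 176, falls inside the course and is skipped): Days 162, 190 and 218 are 14, 14 and 42 days from 176. The tie goes to the later, Day 190.
- Result: 1 of 5 sets kept, shown as FU3.

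**All start days, visits on target.** For RT1 on Days 121 to 637 (517 starts), 481 keep 1 of 5 sets and 36 keep none. For vital signs, 52 keep 1 of 13 visits and 465 keep 2. Restricted to Days 127 to 637 (at least 7 days after FU2; 511 starts), the means are 475/511 = 0.93 sets and (46×1 + 465×2)/511 = 1.91 vital-sign visits.

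**Visits within tolerance.** Two sets can survive. Take FU4 on Day 262, RT1 on Day 270, RTFU on Day 354 and FU5 on Day 363. Distances to 267 are 5 (FU4) and 3 (RT1); distances to 358 are 4 (RTFU) and 5 (FU5). Both RT1 and RTFU are kept. In simulation this happened in about 13–15% of courses (course starting 1–14, 7–28 or 1–90 days after the triggering visit, all dates uniform within tolerance).

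**Why 2 is the ceiling.** A course runs at most 84 + 3 = 87 days from RT1.
- Starting in a 91-day window, it reaches at most one further row.
- Starting in FU3, it ends by Day 221 + 87 = 308, before the FU5 row opens on Day 313.
- Starting in FU2, it touches three rows only if RT1 is on Day 222 − 87 = 135 or later. RT1 is then at least 15 days from target 120, and an attended FU2 (at most 3 days off) takes that row.

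If FU2 vital signs are missing, 3 of 13 can survive (RT1 on Days 138 to 148, nominal timing).

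**Other tests.** Urinalysis has 4 sets per course and none at FU2, so 2 of 4 survive for starts on Days 121 to 148. Coagulation is absent from the text of Protocol 10.1.11 but present in the schedule tables; if it is not drawn at FU3 to FU9, 2 of 5 survive for 465 of 517 starts.

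**Unscheduled draws.** Take one draw on a uniformly random day from 82 to 736 (655 days), with the scheduled visit attended.
- Visits on target: only the 9 target days themselves can qualify, 9/655 = 1.4%.
- Visits uniform within ±k days: the number of draw days that beat the visit averages Σ(4j−1)/(2k+1) over j = 1 to k. This is 21/7 = 3 for k = 3 and 406/29 = 14 for k = 14. In total (2×3 + 7×14)/655 = 104/655 = 15.9%.

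**The case against.** The strongest reply is that nothing in the SAP maps RT visits into follow-up rows. SAP 5.2 makes them scheduled visits, SAP 13.5 and 13.6 tabulate by scheduled visit, and the table shells are a separate document, so separate RT rows would fit the wording. This stands: a reader might infer that the SAP orders re-treatment safety data to be discarded, and it does not. What remains is that the SAP gives no rule for RT rows, and its one rule, followed literally, produces the result above.

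Other inferences also go too far.
- *That no more than 1 of 5 sets can survive.* This is true only with follow-up visits on target.
- *That the shift tables use windowed values.* SAP 13.5 does not say which value they use.
- *That SAP 12.1 is flatly contradicted.* The sentence sits in the efficacy section. If it also governs safety data, literal use of Table 2 conflicts with it; if not, there is no conflict.
- *That the open-label safety conclusion would rest on a sliver of the data.* Out-of-range laboratory values remain listed, adverse event tables (including maximum CTCAE grade) are not windowed, and ECGs are summarised at every recorded time.

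These safeguards are partial. Protocol 12.1 limits adverse event reporting of laboratory and vital-sign changes to clinically significant ones with symptoms or needing intervention, and vital signs have no specified listing. Omitting unscheduled values from by-visit means is ordinary practice; the gap there is the lack of a specified worst-value summary. Rollover re-treatment data are listing-only because of SAP 12.1, not Table 2.

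**Conclusion.** The point holds as an unresolved gap with a measurable consequence. If Table 2 is applied literally to randomized Cohort 3 subjects, on-drug values are labelled as follow-up visits. By-visit tables then keep usually 1 and at most 2 of 5 chemistry/haematology sets per course and, with FU2 attended, at most 2 of 13 vital-sign visits. So at least 3 of 5 sets and 11 of 13 visits drop out. Few unscheduled laboratory draws from Day 82 on are kept.

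The size rests on mapping RT visits into Table 2, on follow-up visits inside a course being skipped, and on attendance within tolerance; the unscheduled figures also assume random timing. The effect is confined to by-visit laboratory and vital-sign summaries in a descriptive study with about 18 subjects planned for Cohort 3, where re-treatment is optional. Because these are primary-endpoint data, it should be settled before the tables are produced.

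**What to change.** 1. Add a second window table anchored on RT1 of each course (RT1 to RT12, RTFU), and tabulate laboratory tests and vital signs by those visits. Keep change from the baseline defined in SAP 8.2.1. Change from the RT1 pre-dose value can be an optional addition; for subjects randomized to OMS721 that value follows earlier exposure, so it should not replace the defined baseline.
2. Exclude values taken from RT1 to RTFU from the FU2 to FU9 rows.
3. State that the laboratory shift table uses the worst post-baseline value from all scheduled and unscheduled assessments, separately for the initial and re-treatment periods.

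The cost is SAP wording and one extra set of safety tables. No new data are needed.

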10.1.3. Treatment Visit 1 (Day 1, approximately 7 days after Screening Visit 2)

This visit is to confirm eligibility, randomize (Cohort 2 and Cohort 3) subjects, and administer the first dose of study drug. Randomization may occur up to 2 days prior to Treatment Visit 1 if necessary for site logistical reasons provided eligibility has been confirmed. Eligible subjects for Cohort 1 will initiate treatment with OMS721. Eligible subjects for Cohort 2 and Cohort 3 will be randomized by the pharmacist or unblinded drug-designee at the study center. A computer-generated randomization will be created allocating Cohort 2 and Cohort 3 subjects to either OMS721 or vehicle.

Prior to administering the dose of study drug, the following procedures will be performed:

1. Review of AEs and concomitant medications, including corticosteroid dose (if applicable).
2. Vital signs including BP, pulse rate, RR, and temperature (after at least 5 minutes of rest).
3. ECG taken (after at least 5 minutes of rest in the supine position).
4. Laboratory samples will be collected for:
 - Hematology, chemistry, coagulation, cystatin C
 - Urinalysis
 - Serum or urine pregnancy test in women of childbearing potential. If the test result is positive then the subject will be excluded from the study
 - Blood samples for future research
 - Serum PK sample
 - Serum PD sample
 - Serum ADA sample
5. For three days prior to Treatment Visit 1, three once daily first void urine samples for albumin/creatinine and protein/creatinine ratios will be collected and brought for analysis at this visit.

Study drug will be administered by IV infusion over 30 minutes.

After dosing with study drug, the following procedures will be performed:

1. Vital signs including BP, pulse rate, RR, and temperature (after at least 5 minutes of rest) at the following timepoints: 30 minutes, 1 hour.

CONFIDENTIAL

No use, disclosure or reproduction outside of Omeros without prior written authorization

2. ECG taken (after at least 5 minutes of rest in the supine position), to be obtained immediately before the 5-minute, post dose PK sample.
3. Serum PK samples at the following timepoints after end of dosing: 5 minutes, 2 hours, and 24 hours (**Day 2**), 72 hours (**Day 4**).
4. Serum PD sample after the end of dosing: 2 hours.
5. The subject may be discharged after arrangements are made for the collection of PK samples on **Days 2 and 4**.

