10.1.4. Treatment Visits 2, 3, 4 (Days 8, 15, 22; +/- 2 days)

Study drug will be administered once per week for a total of 12 weekly doses during the study. The following procedures will be performed at Treatment Visits 2, 3, and 4:

Prior to administering the dose of study drug, the following procedures will be performed:

1. Vital signs including BP, pulse rate, RR and temperature (after at least 5 minutes of rest).
2. AEs and concomitant medications, including corticosteroid dose (if applicable) will be recorded.
3. Laboratory samples will be collected for:
 - Hematology, chemistry, coagulation, cystatin C
 - Urinalysis
 - Urine for inflammatory biomarkers (visit 4 only)
 - Blood samples for future research
 - Serum PK sample
 - Serum PD sample

Study drug will be administered by IV infusion over 30 minutes.

After dosing with study drug, the following procedures will be performed:

1. Vital signs will be taken including BP, pulse rate, RR, and temperature (after at least 5 minutes of rest) at the following timepoint: 30 minutes.
2. Serum PK samples will be taken at the following timepoint: 30 minutes (visit 2 and visit 3 only).
3. Serum PD samples will be taken at the following timepoint: 30 minutes (visit 2 and visit 3 only).
4. At Treatment Visit 4, provide subjects with supplies to collect first void urine samples for urine albumin/creatinine and protein/creatinine ratios on three mornings prior to Treatment Visit 5.

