13.6. Vital Signs

Summary statistics for actual values and change from baseline will be tabulated for vital signs by disease group, cohort and treatment at each scheduled visit.

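### Applied literally, the SAP's one-value-per-window rule leaves the by-visit vital-sign tables with no pre-dose readings at Treatment Visits 2 to 12

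*SAP*

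**What the plan says.** **Selection rule.** SAP 8.2.3, Table 2, assigns assessments to visits by windows in whole days. Where a window holds several readings, its footnote 1 takes only the one nearest the target day. For ties it adds: "If there are 2 assessments that are equally spaced from the target day, the latter will be used in the analysis". It names no data type and no exception for measurements planned more than once on the same day.

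**Study day.** SAP 8.1 defines it from calendar dates: "Event Date – First Dose Date + 1 if the event date is on or after the first dose date". Clock time plays no part.

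**Baseline.** For vital signs SAP 8.2.1 applies its general rule: "the baseline value is defined as the last non-missing value prior to the first study drug administration". When it is recorded, that is the pre-dose reading at Treatment Visit 1 (T1).

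**What is measured.**
- At T1, Protocol 10.1.3 schedules vital signs before dosing and then "at the following timepoints: 30 minutes, 1 hour".
- At T2 to T4, Protocol 10.1.4 lists vital signs under "Prior to administering the dose of study drug, the following procedures will be performed", and again after dosing: "Vital signs will be taken including BP, pulse rate, RR, and temperature (after at least 5 minutes of rest) at the following timepoint: 30 minutes". Sections 10.1.5 to 10.1.8 repeat this pattern through T12.
- Follow-Up Visits 1 and 2 (FU1, FU2) have one set each. Protocol 10.1.11 schedules none at the Cohort 3 extended follow-up visits.

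**How it is tabulated.** SAP 13.6 says: "Summary statistics for actual values and change from baseline will be tabulated for vital signs by disease group, cohort and treatment at each scheduled visit". Protocol 13.2.10.5 is also by scheduled visit. Neither mentions a time point within the visit.

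**The concern.** Two rules that are each reasonable combine badly. A nearest-day rule with a later-on-tie clause suits repeat or off-schedule visits. When several readings are planned for one dosing day, every one of them is equally far from the target day. The clause then always selects the last.

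The effect is on what the tables mean. Each on-treatment change from baseline would be a post-infusion reading minus a pre-infusion one: 1 hour after dosing at T1, 30 minutes after dosing at T2 to T12, and untimed at FU1 and FU2. A reader could not tell whether a change at a dosing visit was an acute response to that day's infusion or had been present before it. A change at 30 minutes after the first exposure that had resolved by 1 hour would not appear at all.

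Vital signs are a named component of the primary safety endpoint (SAP 6). Protocol 12.1 makes a vital-sign change an adverse event only if it is clinically significant and also symptomatic or in need of intervention, so silent changes would show mainly in these tables. SAP 13.6 provides no listing or shift table for vital signs; SAP 13.5 provides both for laboratory values. Cohort 1, about 16 of 44 planned subjects, has no vehicle arm.

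**Working it through.** The plan gives no figure of its own on this point, so the check is a count. A set here means the blood pressure, pulse, respiratory rate and temperature taken together at one time.

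**Inputs.** Scheduled sets come from Protocol 10.1.3 to 10.1.10 and the schedule in Protocol 19.2. The windows and selection rule come from SAP Table 2, and the study-day formula from SAP 8.1. The T1 pre-dose set is taken as baseline and is not counted as post-baseline.

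**Step 1: sets scheduled after baseline.**

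| Visits | Sets per visit | Post-baseline sets |
|---|---|---|
| T1 | 30 minutes, 1 hour | 2 |
| T2 to T12 (11 visits) | pre-dose, 30 minutes | 11 × 2 = 22 |
| FU1, FU2 | one each | 2 |
| Total | | 2 + 22 + 2 = 26 |

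**Step 2: apply footnote 1.** For a visit held on day *v* with target day *D*, every reading that day is |*v* − *D*| days from target. The distances are equal whatever *v* is, so the tie clause decides and the last reading is kept.

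| Visits | Kept | Dropped |
|---|---|---|
| T1 | 1-hour (1) | 30-minute (1) |
| T2 to T12 | 30-minute (11) | pre-dose (11) |
| FU1, FU2 | the single set (2) | none |
| Total | 1 + 11 + 2 = 14 | 1 + 11 = 12 |

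The share dropped is 12/26 = 46%, including 11 of the 11 post-baseline pre-dose sets.

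**Step 3: does visit timing matter?** It does not within the permitted windows. Treatment visits may move by 2 days, and from T3 on the SAP windows are the target day ± 3. T2 on Days 6 to 10 lies inside Days 2 to 11. FU1 on Days 82 to 88 lies inside 82 to 102, and FU2 on Days 117 to 123 inside 103 to 148. Moving each visit after T1 at random by up to 2 days, 2,000 times, always kept the eleven 30-minute sets at T2 to T12 and never a pre-dose set.

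**Step 4: does another section restore the time points?**
- SAP 13.8 summarises ECG parameters for every time recorded.
- SAP 15 summarises lectin pathway activity for each scheduled time point.
- SAP 13.6 has no such wording for vital signs.

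**Step 5: with the fix.** If selection is made within visit and nominal time point, all 26 sets are kept: 11 pre-dose, 12 at 30 minutes, 1 at 1 hour and 2 in follow-up.

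**The case against.** The best defence is that footnote 1 was never meant to make planned pre-dose and post-dose readings compete. Table 2 maps days to visits, and its natural use is for two attendances falling around one target day. The schedule in SAP 5.1 has separate rows for pre-dose, 30-minute and 1-hour vital signs, so one assessment may mean one of each. Applied to everything, the literal reading would also defeat the ECG and pharmacodynamic summaries and the averaging of three urine samples. SAP 20.1 keeps the table shells in a separate document, which may already carry rows by time point.

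This makes a per-time-point reading possible. It does not make it the written rule. The ECG, pharmacodynamic and urine sections each state how multiple values are handled, and the vital-sign section does not. Even if footnote 1 is set aside, SAP 13.6 still does not say which of two or three readings fills a visit row.

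Other points stand in part:
- The vehicle arms of Cohorts 2 and 3 would show a shift caused by the infusion procedure itself. They would not show whether a drug-related shift is acute or sustained.
- No test or decision rule uses these tables; the study is descriptive.
- A pre-dose set is kept when that day's post-dose set is missing.
- The tie clause speaks of two assessments while T1 has three on one day. Treating the first as baseline leaves two, which is an interpretive step.

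A reader might infer that pharmacokinetic summaries lose their pre-dose values in the same way. SAP 14 does not support that. It uses actual sampling times in all pharmacokinetic analyses and protocol times for mean-concentration graphs, and its non-compartmental analysis needs serial samples.

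**Conclusion.** The point holds as a defect in the written rule. Followed literally, with complete data through FU2, it keeps 14 of 26 scheduled post-baseline vital-sign sets and drops 12 from the by-visit tables. The remaining on-treatment rows mix 1-hour and 30-minute readings against a pre-dose baseline, so the tables cannot separate an acute post-infusion change from a sustained one.

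This rests on three assumptions: footnote 1 applies to vital signs as written, both readings are present at each dosing visit, and the T1 pre-dose reading is the baseline. The count stops at FU2 and does not cover Cohort 3 re-treatment courses.

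Two stronger conclusions are tempting and not supported. One is that the readings are lost: they remain in the database, and the unseen shells may already display them, so their absence from the final tables is not established. The other is that reported blood pressure is off by some known amount: the documents give no size for any infusion effect, so none can be stated.

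**What to change.** Make two wording changes in the SAP.

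1. In Table 2, footnote 1, state that the nearest-day and later-on-tie rules apply within each visit and nominal time point, not across time points.
2. In SAP 13.6, tabulate vital signs by visit and nominal time point (pre-dose, 30 minutes, 1 hour), each with change from baseline.

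A post-dose minus same-visit pre-dose change would show the acute response directly. It is an optional extra display, since neither document promises it.

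The data are already scheduled for collection, so the cost is some additional table rows. If the shells already split by time point, the change only brings the SAP text into line with them.
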